11.7 Safety Analyses

All analyses of safety data will use the randomized population.

11.7.1 Analysis of MACE and Expanded MACE Components

The primary safety endpoint, time to the first adjudicated MACE, will be analyzed as [date of the first MACE minus the date of randomization + 1]. A MACE is defined as all-cause mortality, non-fatal myocardial infarction, or non-fatal stroke. Subjects who have not experienced a MACE by study closure will be censored on the date of their last study assessment. The hazard ratio (vadadustat/darbepoetin alfa) and its 95% CI will be obtained from a stratified Cox proportional hazards model. As this study has not been designed to provide a stand-alone assessment of MACE, this analysis will be considered a descriptive analysis. A similar analysis as described for the primary analysis of the MACE endpoint will be performed with censoring of subjects 4 weeks following discontinuation of study medication if they did not have a MACE prior to that time.

The following safety endpoints will also be summarized using time to event methods as for MACE:

1. Individual components (all-cause mortality, non-fatal myocardial infarction, non-fatal stroke) of MACE.
2. Thromboembolic events (defined as arterial thrombosis, DVT, PE, or vascular access thrombosis).
3. Hospitalization for heart failure (HF).
4. Expanded MACE, defined as all-cause mortality, non-fatal myocardial infarction, non-fatal stroke, hospitalization for HF, or thromboembolic event.

For these endpoints the incidence ("yes"/"no") of the endpoint will be presented for each treatment arm. Kaplan-Meier curves will be presented for each endpoint as the time of endpoint free survival (ie, time until endpoint or death).

The primary MACE analysis will be based upon all events that accrue over the 2 DD-CKD studies (Studies AKB-6548-CI-0016 and AKB-6548-CI-0017) (see [Section 11.1.2, Sample Size for the Primary Safety Endpoint](#)).

The SAP for this pooled MACE assessment in DD-CKD subjects provides details of the primary analyses for MACE, for individual components of MACE, and for an expanded version of MACE. Details of sensitivity analyses and subgroup analyses are also provided in the MACE SAP.

11.7.2 Analysis of Adverse Events

Adverse events will be summarized using the number and percentage of subjects with AEs for all subjects in the safety population. Summaries will also be provided for subgroups including Region, Age, Gender and Race.

All AEs will be coded using MedDRA. Treatment-emergent and post-treatment AEs will be summarized by System Organ Class and Preferred Term for each treatment group. Adverse events will also be summarized by their maximum severity.

Summaries will also be provided for the following types of AEs:

- SAEs.
- Related AEs (including all categories for relationship to study medication other than “Unrelated”, as determined by the Investigator).
- AEs leading to early discontinuation of study medication.

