7.5 Study Completion, Subject Completion, Study Discontinuation, and Withdrawal of Subjects

7.5.1 Study Completion

The study will be considered completed (end of trial) when approximately 631 MACE events have accrued over the 2 DD-CKD studies (Studies AKB-6548-CI-0016 and AKB-6548-CI-0017) and all enrolled subjects have had the opportunity to have their Visit 13 (+/- 5 days). These 2 DD-CKD studies were sized based on power considerations for the primary safety analysis of MACE, and thus each study is highly powered (>90%) for the primary and key secondary efficacy analysis. Thus, primary efficacy analyses will be based on the randomized population and every subject will have completed (or had the opportunity to complete) the primary evaluation period (Weeks 24-36).

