7.5.5 Individual Subject Discontinuation

During this study, it is anticipated that some subjects may permanently discontinue study medication (vadadustat or darbepoetin alfa) for any of the following reasons:

- Unacceptable toxicity or drug intolerance
- Investigator discretion
- Subject withdrawal of consent
- Subject becomes pregnant
- Subject receives kidney transplant
- Lack of efficacy
- Other reasons.

Lack of efficacy is defined as inadequate response to darbepoetin alfa or vadadustat in the Investigator's opinion.

Subjects who undergo a solid organ (including kidney), hematopoietic stem cell, or bone marrow transplantation will have their study medication (vadadustat or darbepoetin alfa) permanently discontinued.

See [Section 9.4, Study Medication Stopping Rules](#) for additional details on the management of subjects with ALT and AST abnormalities.

It is important to continue to follow subjects that permanently discontinue study medication. Please see [Section 7.5.5.1, Temporary Interruption of Study Medication](#) and [Section 7.5.5.2, Permanent Discontinuation of Study Medication](#), and [Appendix A: Schedule of Activities](#).

Receipt of rescue therapy is not a reason for permanent study medication discontinuation. While receiving ESA rescue, subjects must temporarily discontinue study medication (vadadustat or darbepoetin alfa), but should resume study medication once rescue therapy has ended, as detailed in [Section 8.4.7, Rescue Therapy](#).

As part of the informed consent process, only subjects who fully understand and agree to full participation and long-term follow-up should be consented to participate.

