9 STUDY PROCEDURES AND SCHEDULE OF ACTIVITIES

Please see [Appendix A: Schedule of Activities](#) for a detailed table of the Schedule of Activities.

This study includes the following visits:

- Optional Prescreening.
- Two Screening visits (SV1 and SV2).
- Baseline/Randomization visit (Week 0/Day 1).
- Year 1 Treatment Period Study Visits/Evaluations while receiving study medication: Weeks 2, 4, 6, 8, 10, 12 (± 3 days), and every 4 weeks thereafter until Week 52 (± 5 days).
- Year 2 Treatment Period Study Visits/Evaluations while receiving study medication: Weeks 64, 76, 88, and 104 (± 10 days).
- Year 3 Treatment Period Study Visits/Evaluations while receiving study medication: Weeks 116, 128, 140, and 156 (± 10 days).
- Year 4 Treatment Period Study Visits/Evaluations while receiving study medication: Weeks 168, 180, 192, and 208 (± 10 days).
- EOT visit (± 7 days).

- Follow-up visit: 4 weeks after the EOT visit (\pm 7 days).
- Unscheduled visit(s).

The following sections describe the procedures to be completed during the study. Subjects are to be assessed by the same Investigator or investigative site personnel whenever possible.

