10.3.1 Reporting Period

The AE reporting period for this study begins from time of randomization through global study completion.

In addition, any AE that occurs subsequent to the AE reporting period that the Investigator assesses as related to the study medication should also be reported as an AE.

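### AE and SAE percentages take no account of time on drug, so they can mislead if discontinuation differs by arm; exposure-adjusted rates should stand beside them

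*Protocol*

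**What the plan says.** In the current protocol (Version 7.0, Amendment 6), Section 11.7.2 says AEs are "summarized using the number and percentage of subjects with AEs". It continues: "Treatment-emergent and post-treatment AEs will be summarized by System Organ Class and Preferred Term for each treatment group". Further summaries cover maximum severity, SAEs, related AEs and AEs leading to early discontinuation. The section contains no subject-year rate, exposure adjustment or common time window, and does not refer to the SAP. Sections 11.7.1 and 11.7.3 do.

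The provisions that set time at risk are these:

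- Section 10.3.1: the AE reporting period "begins from time of randomization through global study completion".
- Section 7.5.1: the study ends at about 631 pooled MACE and once "all enrolled subjects have had the opportunity to have their Visit 13". Appendix A places Visit 13 at Week 36.
- Section 9: the schedule reaches "Year 4 Treatment Period Study Visits/Evaluations while receiving study medication: Weeks 168, 180, 192, and 208".
- Section 7.5.5: permanent discontinuation is anticipated. Listed reasons include intolerance, investigator discretion and lack of efficacy, the last judged by the investigator.
- Section 7.5.5.4: after discontinuation, visits and assessments are flexible. End-of-study status is the one required item; AE assessment is listed only as part of optimal collection.
- Section 11.7.1: MACE, its components, thromboembolic events, heart-failure hospitalization and expanded MACE are analysed by time-to-event methods. MACE is also analysed with censoring 4 weeks after stopping drug.

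**The concern.** A crude percentage depends on both how often events occur and how long subjects are at risk. If one arm stops study drug earlier, fewer of its subjects have a treatment-emergent event at the same underlying rate. Equal drugs can then look different, and a worse drug can look equal.

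Treatment is open-label, and the decision to stop rests partly on investigator judgement, so discontinuation could differ between arms. After stopping, AE information may also become less complete. Appendix A, footnote [w], sends two signals: it has AEs reported through global study completion and also recorded through the follow-up visit. For a subject who stops early, that visit falls 4 weeks after end of treatment, possibly long before global completion.

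At stake is how the general AE and SAE tables will be read. Side-by-side percentages by arm invite comparison even though no test is planned.

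**Working it through.** **The plan's own figure.** Section 11.7.2 states no number. The figure that sets the length of follow-up is 631 events (Section 11.1.2), and it reproduces: 4 × (1.960 + 0.842)² / (ln 1.25)² = 631, for 80% power, margin 1.25, two-sided 95% CI and 1:1 allocation.

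**Inputs from the protocol.** Shortest planned opportunity is 36 weeks; last scheduled visit is Week 208; about 150 subjects per arm.

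**Inputs assumed.** The protocol gives no AE rate, no discontinuation rate and no exposure by arm. Those values below are illustrations. The hazard is taken as constant.

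**Formula.** Percentage with a first event = 1 − exp(−rate × time).

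1. *Spread of follow-up.* At 0.3 first events per year: 1 − exp(−0.3 × 36/52) = 18.8% at 36 weeks; 1 − exp(−0.3 × 4) = 69.9% at 208 weeks. The percentage has no fixed time frame.

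2. *Does the spread alone distort the contrast?* Give both arms follow-up spread evenly over 36 to 156 weeks (the upper limit is assumed), no discontinuation and 0.3 per year: 41.4% in both arms. It does not.

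3. *Equal rates, unequal time on drug:*

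| Rate per year | 1.0 y | 1.25 y | 1.5 y |
|---|---|---|---|
| 0.1 | 9.5% | 11.8% | 13.9% |
| 0.3 | 25.9% | 31.3% | 36.2% |
| 0.5 | 39.3% | 46.5% | 52.8% |
| 1.0 | 63.2% | 71.3% | 77.7% |

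At 0.3 per year, 1.0 versus 1.5 years is about 39 versus 54 subjects of 150 (0.259 × 150; 0.362 × 150).

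4. *Discontinuation modelled directly.* Use the follow-up spread of step 2, discontinuation at 0.4 versus 0.2 per year and an equal event rate of 0.3. The percentage is the average over follow-up x of r/(r + d) × [1 − exp(−(r + d)x)]. Mean time on drug is 1.26 versus 1.51 years, and the percentages are 29.8% versus 34.8%. With discontinuation at 0.3 versus 0.2, they are 32.1% versus 34.8%.

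5. *Masking.* Rate 0.375 for 0.8 years against 0.3 for 1.0 year, a true ratio of 1.25: 0.375 × 0.8 = 0.3 × 1.0, so both arms show 25.9%.

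6. *What the added rate shows.* Person-time to first event or end of exposure is (1 − exp(−rate × time))/rate. In step 3 at 0.3 per year: 0.259/0.864 and 0.362/1.208, both 30 per 100 subject-years. In step 5: 0.259/0.691 = 37.5 against 0.259/0.864 = 30 per 100, which recovers the ratio of 1.25.

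**The case against.** Several counter-arguments have weight.

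- *Follow-up spread is balanced by design.* A reader might infer that follow-up ranging from 36 weeks to several years makes the arms incomparable. The documents do not support that. Allocation is concurrent, stratified and 1:1, and both arms close together; step 2 gives identical percentages. Distortion needs a difference between arms, which the protocol permits but does not predict. The completed 16-week vadadustat hemodialysis study (Section 4.2), where 69 of 94 subjects finished, shows material non-completion but has no comparator rate.
- *No comparison is specified.* Section 11.7.2 summarizes and gives no test, interval or decision rule. That stands; the issue is how the tables will be read.
- *Key outcomes are protected.* This stands fully. The main cardiovascular safety endpoints account for time at risk under Section 11.7.1, so no wider claim about the trial's safety conclusions is justified.
- *AE reporting continues after drug is stopped.* Section 10.3.1 says so, and treatment-emergent and post-treatment events are summarized separately. The concern therefore falls chiefly on treatment-emergent events. That capture becomes thinner after stopping is an inference from Section 7.5.5.4, not a statement in it.
- *Rates have their own weaknesses.* If events are under-recorded after discontinuation while person-time keeps accruing, a rate is biased too. Ending person-time with the treatment-emergent window avoids this, but the rate then assumes that stopping is non-informative.
- *The SAP may add rates.* It may. The point rests on the measure that Section 11.7.2 itself fixes without deferring elsewhere.

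**Conclusion.** The point holds in a limited form. The percentages are a legitimate description, but as the only stated summary of general AEs and SAEs they can understate events in whichever arm has shorter time on drug, mainly for treatment-emergent events. No trial-specific size can be computed. Under the assumed rates of 0.1 to 1.0 per year, 1.0 versus 1.25 years on drug produces spurious gaps of about 2 to 8 points, and 1.0 versus 1.5 years about 4 to 15 points. A 25% higher true rate can disappear altogether. If time on drug proves similar in the two arms, the effect is negligible. The change should be made, but it does not bear on the primary efficacy result or on the time-to-event safety endpoints.

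**What to change.** Keep the percentages. In Section 11.7.2, for treatment-emergent AEs, SAEs, related AEs and AEs leading to discontinuation, add:

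- subjects with a first event per 100 subject-years at risk, with person-time ending at the first event or at the end of the treatment-emergent window;
- the rate difference with its 95% CI;
- time on study drug by arm, shown with the AE tables.

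State the risk window and the denominator with the rates. The denominator needs settling in any case: Section 11.7 assigns all safety analyses to the randomized population, whereas Section 11.7.2 uses the safety population.

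The cost is extra table columns, built from dates already collected. The rates assume a roughly constant hazard and non-informative stopping, and a footnote should say so. If the SAP already provides these rates, aligning Section 11.7.2 with it is enough.

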11.7.3 Remaining Safety Endpoints

The analysis of the following safety endpoints will be detailed in the SAP:

The analysis of proportion of subjects with Hb >12.0 g/dL, >13.0 g/dL, or >14.0 g/dL post-Baseline will classify a subject as a “yes” if:

- Any value Hb >12.0 g/dL at any time after Day 1.
- Any confirmed value Hb >12.0 g/dL at any time after Day 1.
- Any value Hb >13.0 g/dL at any time after Day 1.
- Any confirmed value Hb >13.0 g/dL at any time after Day 1.
- Any value Hb >14.0 g/dL at any time after Day 1.
- Any confirmed value Hb >14.0 g/dL at any time after Day 1.

A Hb value above a set threshold will be considered as confirmed if there are 2 consecutive values above that threshold. The second of the 2 consecutive assessments should be done at most 12 weeks after the first assessment. Subjects with no available data post-Baseline will be excluded from this analysis. All other subjects will be classified to the “no” category.

The analysis of proportion of subjects with any Hb increase >1.0 g/dL within any 2-week interval or >2.0 g/dL within any 4-week interval post-Baseline will classify a subject as a “yes” if at least 1 of the following criteria at any point after Day 1 is met:

- Hb increase >1.0 g/dL within any 2-week interval.

- Hb increase >2.0 g/dL within any 4-week interval.

Subjects with no available data post-Baseline will be excluded from this analysis. All other subjects will be classified to the “no” category.

Observed values of continuous and categorical parameters and changes from Baseline for continuous parameters to each study visit will be summarized descriptively for vital signs and clinical laboratory results. Graphical displays of selected laboratory parameters will also be provided.

11.8 Additional Assessments

11.8.1 Concomitant Medications

Prior and concomitant medications will be coded using World Health Organization (WHO) Drug dictionary.

Prior medications will be defined as any medications that were taken before the date of the first dose of study medication. Concomitant medications will be defined as any medications taken at any time from the date of the first dose of study medication through the date of the last dose of the study medication.

11.8.2 Biomarkers

Biomarkers (including, but not limited to, hepcidin and VEGF) will be summarized descriptively at Baseline and by visit post-Baseline.

11.8.3 Pharmacokinetics

Descriptive and graphical summaries will be generated for PK measurements.

12 DATA HANDLING AND RECORD KEEPING

12.1 Case Report Forms/Electronic Data Capture

This study will utilize an EDC system to manage data collection during this trial. The system is fully Code of Federal Regulations 21 part 11 compliant. An EDC system contains certain functionality including, but not limited to, a graphical user interface to help facilitate data entry, a data validation element to check user data, and a reporting function to assist with the review and analysis of data. Case report forms available through this system are required and should be completed for each randomized subject.

Any form of data from the electronic system are the sole property of the Sponsor and should not be made available in any form to third parties, except for authorized representatives of the Sponsor or appropriate regulatory authorities, without written permission from the Sponsor.

The Investigator has ultimate responsibility for the accuracy, authenticity, and timely collection and reporting of all clinical, safety, and laboratory data entered in the EDC or any other data collection forms. The CRFs must be signed electronically by the Investigator to attest that the data contained on the CRFs is true.

In most cases, the source documents are contained in the subject's chart at the hospital or the physician's office. In these cases, data collected on the CRFs must match the data in those charts.

12.2 Record Retention

To enable evaluations and/or audits from regulatory authorities or the Sponsor, the Investigator agrees to keep records, including the identity of all participating subjects (sufficient information to link records, eg, CRFs and hospital records), all original signed informed consent forms, copies of all CRFs, SAE forms, source documents, detailed records of drug disposition, and adequate documentation of relevant correspondence (eg, letters, meeting minutes, and telephone calls reports). The records should be retained by the Investigator according to the International Council for Harmonisation (ICH), local regulations, or as specified in the Clinical Study Agreement, whichever is longer.

If the Investigator becomes unable for any reason to continue to retain study records for the required period (eg, retirement and relocation), the Sponsor should be prospectively notified. The study records must be transferred to a designee acceptable to the Sponsor, such as another Investigator, another institution, or to the Sponsor. The Investigator must obtain Sponsor's written permission before disposing of any records, even if retention requirements have been met.

13 QUALITY CONTROL AND QUALITY ASSURANCE

13.1 Investigative Site Monitoring Visits

During study conduct, the Sponsor or its agent will conduct periodic monitoring visits to ensure that the protocol and Good Clinical Practice (GCP) are being followed. The monitors will review source documents to confirm that the data recorded on the CRFs is accurate. The Investigator/institution will allow the Sponsor's monitors or designees and appropriate regulatory authorities direct access to source documents to perform this verification.

The investigative site may also be subject to quality assurance audits performed by the Sponsor or companies working with or on behalf of the Sponsor, and/or review by the IRB/IEC, and/or to inspection by appropriate regulatory authorities.

It is important that the Investigator(s) and their relevant personnel are available during the monitoring visits and possible audits or inspections and that sufficient time is devoted to the process.

13.2 Protocol Deviations

The Investigator will not deviate from the protocol, except where necessary to eliminate an immediate hazard to study subjects. Should other unexpected circumstances arise that will require deviation from protocol-specified procedures, the Investigator will consult with the Sponsor or designee (and IRB or IEC, as required) to determine the appropriate course of action.

The investigative site will document all protocol deviations in the subject's source documents. In the event of a significant deviation, the investigative site will notify the Sponsor or its designee (and IRB or IEC, as required). Significant deviations include, but are not limited to,

those that involve fraud or misconduct, increase the health risk to the subject, or confound interpretation of primary study assessments.

14 STUDY DISCONTINUATION/INVESTIGATIVE SITE TERMINATION

The Sponsor reserves the right to discontinue the study prior to inclusion of the intended number of subjects but intends only to exercise this right for valid scientific or administrative reasons. After such a decision, the Investigator must contact all participating subjects within a time period specified by the Sponsor to inform them of the decision to discontinue the study.

14.1 Criteria for Premature Termination or Suspension of the Study

The following criteria may result in either temporary suspension or early termination of the study:

- New information regarding the safety or efficacy of the study medication that indicates a change in the known risk/benefit profile for the compound, such that the risk/benefit is no longer acceptable for subjects participating in the study.
- Significant violation of GCP that compromises the ability to achieve the primary study objectives or compromises subject safety.

The Sponsor reserves the right to discontinue the study for other valid administrative reasons.

14.2 Criteria for Premature Termination or Suspension of Investigational Study Sites

A study site may be terminated prematurely or suspended if the study site (including the Investigator) is found to be in significant violation of GCP, protocol, contractual agreement, or is unable to ensure adequate performance of the study.

14.3 Procedures for Premature Termination or Suspension of the Study or Investigational Sites

In the event that the Sponsor elects to terminate or suspend the study or the participation of an investigational study site, a study-specific procedure for early termination or suspension will be provided by the Sponsor; the procedure will be followed by applicable investigational study sites during the course of termination or study suspension.

